# 5.3. Additional Dosing Guidelines for Pharmacokinetic Sampling

In an effort to standardize food intake for the PK assessments, patients will be asked to consume one can of Ensure® or equivalent, prior to the dose of study drugs (within 30 minutes) on days with pre- and post-dose PK assessments as outlined in Section 7.3.3. Note that valganciclovir and nanatinostat should be taken at the same time, including on Cycle 1 Day 1. An Ensure® equivalent is defined as any liquid nutrition that is at least 8 ounces in size containing at least 8 grams of protein and at least 6 grams of fat. Alternatively, patients may consume a light breakfast in place of consuming an Ensure® equivalent and should start the meal 30 minutes before administration of valganciclovir and nanatinostat.

See Section 5.5.3 for medications to be used with caution with valganciclovir.

# 5.4. Dose Modifications of Nanatinostat and Valganciclovir

For patients who do not tolerate the protocol-specified dosing schedule, or develop toxicities, dose adjustments are permitted to allow the patient to continue study treatment. Dose adjustments, except for valganciclovir adjustments based on renal function (Section 5.4.1) must be approved by the Medical Monitor or Sponsor prior to implementing. These changes must be accurately recorded in the eCRFs.

Given the expectation that both study drugs are required for activity, both agents will be held and restarted in parallel. Requirements for dose modifications and criteria for resumption of dosing are presented in Table 3.

**Table 3:** Dose Modification Guidelines for Study Treatment-Related Toxicity

NCI CTCAE v5.0 Toxicity Grade	Action to be Taken with Study Drugs
Grade 4 neutropenia (ANC $< 0.5 \times 10^9/L$ )	
 
Interrupt nanatinostat/valganciclovir dosing.
 
Resume nanatinostat/valganciclovir at the same doses when ANC ≥1.0 × 10^9/L.
 

NCI CTCAE v5.0	
Toxicity Grade	Action to be Taken with Study Drugs
	
 
If the grade 4 neutropenia lasts more than 7 days or recurs, then reduce valganciclovir to 450 mg orally daily. If the reduced dose is tolerated for ≥4 weeks, then the valganciclovir dose may be increased to 900 mg daily.
 
Use of growth factors (G-CSF, GM-CSF) is permitted as per the ASCO
 

	2015 clinical practice guidelines (Smith 2015).
Grade 3 neutropenia (ANC $0.5 - <1.0 \times 10^9/L$ )	
 
If persistent (>7 days) then interrupt nanatinostat/valganciclovir dosing. Resume nanatinostat/valganciclovir at the same doses when ANC ≥1.0 × 10^9/L. If recurs and persists >7 days, then consider reducing valganciclovir to 450 mg orally daily.
 
Use of growth factors (G-CSF, GM-CSF) is permitted as per the ASCO 2015 clinical practice guidelines (Smith 2015).
 

Grade 4 thrombocytopenia (Platelet count <25 × 10  /L)	Interrupt nanatinostat/valganciclovir dosing.  Interrupt nanatinostat/valganciclovir dosing.
(Platelet count <25 × 10  /L)	• If thrombocytopenia resolves to ≤Grade 2 (>50 × 10  /L), then restart both drugs.
	• If recurs, then consider reducing valganciclovir to 450 mg orally daily.
Grade 3 anemia	Interrupt nanatinostat/valganciclovir dosing.
(Hemoglobin <8.0 g/dL)	• If anemia resolves to ≤Grade 2 (≥8.0 g/dL), then restart both drugs.
	• If recurs, then consider reducing valganciclovir to 450 mg orally daily.
Febrile neutropenia	Interrupt nanatinostat/valganciclovir dosing.
(ANC <1.0 × $10^9$ /L, with a single temperature of $\ge 38.3^\circ$ C or	• Resume nanatinostat/valganciclovir at the same doses when ANC ≥1.0 × 10  /L.
a sustained temperature of ≥38°C for more than 1 hour)	• Use of growth factors (G-CSF, GM-CSF) is permitted as per the ASCO 2015 clinical practice guidelines (Smith 2015).
QTc prolongation	For QTc interval >450 msec and ≤480 msec: Check magnesium and potassium levels and correct any abnormalities. If possible, stop any medications that may prolong the QTc interval. Continue nanatinostat/valganciclovir at the same dose.
	For QTc interval >480 msec and <500 msec: Check magnesium and
	potassium levels and correct any abnormalities. If possible, stop any medications that may prolong the QTc interval. Decrease nanatinostat to 10 mg once daily, days 1 to 4/7 for the remainder of the cycle. Resume nanatinostat/valganciclovir at the initial dose in the next cycle provided that the QTc interval improves to $\leq$ 470 msec at the start of that cycle. Otherwise continue nanatinostat at 10 mg once daily, days 1–4/7.
	For QTc interval >500 msec: Check magnesium and potassium levels and correct any abnormalities. Interrupt nanatinostat/valganciclovir dosing and stop any medications that may prolong the QTc interval. If the QTc interval improves to ≤470 msec just prior to the start of the next cycle, resume nanatinostat/valganciclovir at the initial dose. If no other cause of QTc prolongation is identified, reduce dose of nanatinostat to 10 mg once daily, days 1-4/7. Otherwise continue to hold nanatinostat/valganciclovir for as long as necessary.
Other study drug-related Grade 3/4 non-hematologic toxicity or Grade 3/4 clinically significant laboratory abnormalities	Grade 4 non-hematologic AE or clinically significant laboratory abnormalities: Discontinue nanatinostat/valganciclovir dosing. Following resolution of the toxicity to ≤Grade 1 or to the patient's baseline value, if the investigator considers it to be in the patient's best interest to resume therapy, this may be permitted at a lower dose level following discussion with Viracta.

NCI CTCAE v5.0 Toxicity Grade	Action to be Taken with Study Drugs
	Grade 3 non-hematologic AE or clinically significant laboratory
	abnormalities: withhold dose until toxicity resolves to ≤Grade 1 and resume
	nanatinostat/valganciclovir at the same dose.

Abbreviations: ANC = absolute neutrophil count; CTCAE = Common Terminology Criteria for Adverse Events; G-CSF = granulocyte colony-stimulating factor; GM-CSF = granulocyte macrophage-colony stimulating factor; NCI = National Cancer Institute; PO = orally; QD = once daily.

Patients should be monitored approximately twice weekly for resolution of the toxicity. During a dose interruption, study days and procedures will continue to accrue until the end of the current cycle (see Schedule of Events in Section 6.1). If the dose interruption extends beyond the end of the cycle, the subsequent cycle will not begin until dosing has resumed. If the dose is held for more than 14 days, the Investigator should consult with the Medical Monitor before dosing resumes.

If a patient has multiple dose interruptions for study drug toxicity or has had to interrupt for more than 14 days, a dose reduction should be considered. Re-escalation of study drug dose may only be performed after approval by Medical Monitor.

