- 15. All acute toxic effects of any prior anti-tumor therapy resolved to Grade ≤1 before initiation of study treatment (excluding alopecia and stable Grade 2 sensory neuropathy).

16. Required baseline laboratory data (within 2 weeks prior to start of study drug administration) as shown in the table below:

System	Laboratory Value
Hematology	
Absolute neutrophil count (ANC)	≥1000/mm³ (no growth factor support within 14 days)
Platelets	≥50,000/mm³ (no platelet transfusion within 14 days)
Hemoglobin	≥8.0 g/dL (no red cell transfusion within 21 days)
Renal	
Creatinine clearance	≥50 mL/min (Cockcroft-Gault)
Hepatic	
Total bilirubin	<pre> ≤2.0 × upper limit of normal (ULN) (except patients with documented Gilbert's syndrome [<3.5 × ULN])</pre>
Aspartate aminotransferase (AST [SGOT]) and alanine aminotransferase (ALT [SGPT])	≤3.0 × ULN (or ≤5.0 × ULN if liver involvement by primary disease)
Coagulation	
International normalized ratio (INR) Activated partial thromboplastin time (aPTT)	≤1.5 × ULN unless participant is receiving anticoagulant therapy (as long as INR or aPTT are within the therapeutic range of intended use of anticoagulants)

- 17. Life expectancy > 3 months.
- 18. Women of childbearing potential (ie, reached menarche, and not premenarchal or post-menopausal [no menses for 12 months without an alternative medical cause, or surgically sterile]) must have the following:
  - a. Understand that the study medication is expected to have teratogenic risk.
  - b. Have a negative serum beta human-chorionic gonadotropin ( $\beta$ -hCG) pregnancy test at screening.
  - c. Commit to true abstinence from heterosexual intercourse: When this is in line with the preferred and usual lifestyle of the patient (Periodic abstinence [eg, calendar, ovulation, symptothermal, post-ovulation methods], declaration of abstinence for the duration of exposure to the investigational medicinal product [IMP], or the withdrawal method are not acceptable forms of contraception). Otherwise, begin a highly effective method of birth control with a Pearl-Index <1%, without interruption, throughout the study dosing period and for 6 months after the last dose of nanatinostat. Apart from abstinence, highly effective methods of birth control include the following:

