# 5.2.2. Valganciclovir Administration

The daily dose of valganciclovir for patients ≥17 years of age is 900 mg orally (continuous treatment) in combination with nanatinostat. Patients with a CrCl 50-59 mL/min at study entry will receive valganciclovir 450 mg orally once daily as per Table 4. Patients will continue to receive nanatinostat plus valganciclovir in 28-day cycles until discontinuation as described in Section 7.2.3.

The daily dose of valganciclovir for patients ≤16 years of age is based on body surface area (BSA) and CrCl derived from a modified Schwartz formula, and is calculated using the equation below:

Adolescent dose (mg) =  $7 \times BSA \times Schwartz$  Creatinine Clearance

$$Mosteller\ BSA\ (m^2) = \sqrt{\frac{Height\ (cm)\ x\ Weight\ (kg)}{3600}}$$
 
$$Schwartz\ Creatinine\ Clearance\ (mL\ /\ min\ /\ 1.73m^2)\ = \frac{k\ x\ Height\ (cm)}{Serum\ Creatinine\ (mg\ /dL)}$$

Note: k value is 0.55 (boys <13 years and girls <16 years) or 0.7 (boys aged 13 to 16 years).

Patients should be monitored for serum creatinine levels regularly, consider changes in height and body weight, and adapt the valganciclovir dose as appropriate. Valganciclovir tablet dose is

determined based on the calculated valganciclovir dose in mg and available tablet strength (450 mg)  $\pm 10\%$  range of the tablet strength. For example, if the calculated dose exceeds 900 mg, a maximum dose of 900 mg should be administered. If the calculated dose is between 900 mg and 810 mg, a 900 mg dose (two 450 mg tablets) should be taken. If the calculated dose is between 809 mg and 405 mg, 450 mg dose (one 450 mg tablet) should be taken.

Adequate hydration should be maintained for all patients. For patients who develop an elevated creatinine while on study, their dose of valganciclovir should be adjusted (see Section 5.4.1).

In patients who are unable to tolerate oral dosing of valganciclovir, the Investigator will have the option of administering ganciclovir intravenously (IV) at 5 mg/kg QD. In patients who are receiving a dose of valganciclovir less than 900 mg orally once daily, the dose of ganciclovir will be reduced accordingly using the ratio of 900 mg valganciclovir to 5 mg/kg ganciclovir.

Valganciclovir absorption is affected by food. Therefore, patients should be instructed to take both valganciclovir and nanatinostat with food and not fasting.

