## 5.4.1. Dose Modifications for Patients with Renal Impairment

Patients ≥17 years of age who develop an elevated creatinine while on study should have their creatinine clearance (CrCl) recalculated and dose of valganciclovir adjusted per Table 4.

An estimated CrCl in adults is calculated from serum creatinine by the following formulas:

For serum creatinine measured in mg/dL:

For males = 
$$(140 - age [years]) \times (body weight [kg]) = XX mL/min$$
  
(72) × (serum creatinine [mg/dL])

For females = 
$$(140 - age [years]) \times (body weight [kg]) = XX mL/min \times 0.85$$
  
(72) × (serum creatinine [mg/dL])

For serum creatinine measured in µmol/L:

For males = 
$$(140 - age [years]) \times (body weight [kg]) \times 1.23 = XX mL/min$$
  
Serum creatinine (µmol/L)

For females = 
$$(140 - age [years]) \times (body weight [kg]) \times 1.23 = XX \text{ mL/min} \times 0.85$$
  
Serum creatinine (µmol/L)

For patients already receiving a dose of valganciclovir lower than that recommended in Table 4, the Investigator should discuss the amount of dose reduction with the Medical Monitor.

Table 4: Valganciclovir Dosing for Patients with Renal Impairment

Creatinine Clearance (mL/minute)	Valganciclovir Dose
≥60	900 mg once daily
40–59	450 mg once daily
25–39	450 mg every 2 days
10–24	450 mg twice weekly
<10 (on hemodialysis)	Not recommended (discuss with Medical Monitor)

Source: Valcyte USPI 2021(Genentech 2021) and SmPC 2018 (Roche 2018)

Note: Patients  $\geq$ 17 years of age receiving hemodialysis (CrCl less than 10 mL/min) cannot use valganciclovir tablets because the daily dose of valganciclovir tablets required for these patients is less than 450 mg. In this case the Investigator will have the option of administering ganciclovir IV at 5 mg/kg QD, after discussion with the Study Medical Monitor.

Patients 12 to 16 years of age who develop an elevated creatinine while on study should have their CrCl recalculated (by a modified Schwartz formula per Section 5.2.2) and dose of valganciclovir adjusted based on body surface area (BSA).

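### Table 3's fixed 450 mg valganciclovir step gives no reduction after a first prolonged Grade 4 neutropenia in patients already on 450 mg daily for renal function

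*Protocol*

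**What the plan says.** Protocol Section 5.4 presents Table 3 as the requirements for dose modification. In the Grade 4 neutropenia row both drugs are interrupted and then resumed at the same doses once ANC reaches 1.0 × 10⁹/L. One further step is mandatory: "If the grade 4 neutropenia lasts more than 7 days or recurs, then reduce valganciclovir to 450 mg orally daily". After at least four weeks tolerated at the lower dose, "then the valganciclovir dose may be increased to 900 mg daily". The row names no other valganciclovir dose.

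The Grade 4 thrombocytopenia and Grade 3 anemia rows use the same target in softer form: "If recurs, then consider reducing valganciclovir to 450 mg orally daily". The Grade 3 neutropenia row also says only to consider it, when the event recurs and persists beyond 7 days.

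Not every patient is on 900 mg. Section 4.1.1, criterion 16, admits patients with CrCl of 50 mL/min or more. Section 5.2.2 says: "Patients with a CrCl 50-59 mL/min at study entry will receive valganciclovir 450 mg orally once daily as per Table 4". Section 5.4.1 re-doses patients aged 17 or over from Table 4 if creatinine rises on study: 450 mg once daily at CrCl 40-59, "450 mg every 2 days" at 25-39, and "450 mg twice weekly" at 10-24. It also calls for a talk with the Medical Monitor, but only about those under the Table 4 dose: "patients already receiving a dose of valganciclovir lower than that recommended in Table 4, the Investigator should discuss the amount of dose reduction".

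The text around Table 3 has four general rules. Dose adjustments other than renal ones need prior approval by the Medical Monitor or Sponsor. A hold of more than 14 days requires consultation before dosing resumes. A reduction should be considered after multiple interruptions or a hold of more than 14 days. Re-escalation needs Medical Monitor approval.

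**The concern.** A reduction rule written as an absolute dose works only for patients who start above that dose. Here an eligible group starts exactly at it, and more patients can reach it during treatment. Table 4 makes 450 mg daily the full dose at CrCl 40-59, as 900 mg daily is at CrCl 60 or more. After the same prolonged Grade 4 neutropenia, the rule therefore halves the renal-adjusted dose in one group and leaves it at 100% in the other.

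What is at stake is patient safety: resuming a drug for which Section 1.2.2 names cytopenias among the notable adverse events, at an unchanged dose, in patients with reduced renal clearance. Sample size, alpha and the primary analysis are not involved.

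**Working it through.** The plan states no figure to reproduce. The check compares the Table 3 target with the dose the patient is already taking, then asks which other rule would apply.

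**Step 1: size of the required reduction.** Weekly dose = mg per dose × doses per week, with every 2 days counted as 3.5 doses per week. The Table 3 target is 450 × 7 = 3,150 mg/week.

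| CrCl (mL/min) | Table 4 dose | Current mg/week | Change the row requires |
|---|---|---|---|
| ≥60 | 900 mg daily | 900 × 7 = 6,300 | (3,150 − 6,300)/6,300 = −50% |
| 40-59 (includes 50-59 at entry) | 450 mg daily | 450 × 7 = 3,150 | (3,150 − 3,150)/3,150 = 0% |
| 25-39 | 450 mg every 2 days | 450 × 3.5 = 1,575 | none defined; already below target |
| 10-24 | 450 mg twice weekly | 450 × 2 = 900 | none defined; already below target |

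The 50-59 group is affected from Cycle 1 Day 1. The lower bands arise only if renal function falls on study.

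**Step 2: does another rule fill the gap?** Take a patient at CrCl 50-59 on 450 mg daily.

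| Rule | Trigger | First episode >7 days, hold ≤14 days | Recurrence | Hold >14 days |
|---|---|---|---|---|
| Section 5.4.1, patients below the Table 4 dose | dose lower than Table 4 | no: the patient is at the Table 4 dose | no | no |
| Section 5.4, approval | a dose adjustment | no: restarting at 450 mg adjusts nothing | no, unless a cut is proposed | no, unless a cut is proposed |
| After Table 3, consultation | hold >14 days | no | only if the hold is >14 days | yes |
| After Table 3, consider a reduction | multiple interruptions or hold >14 days | no | yes, no dose named | yes, no dose named |

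Only the first column is wholly uncovered. A 900 mg patient with the same episode must be halved, and that adjustment goes to the Medical Monitor or Sponsor for approval. The 450 mg patient meets no trigger.

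**Step 3: size of the proposed step.** From 450 mg daily to every 2 days: (3,150 − 1,575)/3,150 = 50%, the same proportion as 900 to 450. From every 2 days to twice weekly: (1,575 − 900)/1,575 = 43%.

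**Step 4: how many patients.** The documents do not give the share on 450 mg daily or less for renal function. If it were 5% to 20% (an assumption), that is 21 × 0.05 to 0.20 = 1.05 to 4.2 of a 21-patient cohort, or 141 × 0.05 to 0.20 = 7.05 to 28.2 of an expanded cohort. Protocol Section 1.2.4 reports Grade 3/4 neutropenia in 12 and Grade 3/4 neutrophil count decreased in 9 of 64 patients, so at most 21/64 = 32.8% if no patient had both. If that pooled rate carried over to renally dosed patients (also an assumption), any Grade 3/4 event would occur in about 0.3 to 1.4 of 21, or 2.3 to 9.3 of 141. The uncovered case is a subset of these: Grade 4, first episode, more than 7 days, hold of 14 days or less.

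**The case against.** The best reply is that the row says to reduce, and an unchanged 450 mg is plainly not a reduction. A careful investigator would notice and call the Medical Monitor, and Section 5.4 permits a lower dose with approval in every case. Even in the uncovered case both drugs are held until ANC recovers, growth factors are allowed, monitoring is about twice weekly, and the investigator may stop treatment. All of this stands and limits the seriousness. It does not close the gap: the row's default is to resume at the same doses, the only lower dose it names is the current one, and nothing requires the call.

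A reader might also infer more than the documents support:

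- That Table 3 tells sites to raise the dose when CrCl is below 40. An instruction to reduce cannot sensibly be read that way. The row simply defines no step there.
- That recurrence, or the other three rows, is equally unprotected. Those rows say only to consider the step, and only on recurrence. The text after Table 3 already asks that a reduction be considered after multiple interruptions, though without a dose.
- That re-escalation to 900 mg is unguarded at CrCl 40-59, where it would be twice the Table 4 dose. The row is silent on renal function, but the step is optional and needs Medical Monitor approval.
- That the Phase 1b valganciclovir cut is a precedent for going below 450 mg daily. That cut was from 900 to 450 mg twice daily, so it ended at 900 mg per day, this trial's full dose.

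**Conclusion.** The point holds in a narrow form. For patients on 450 mg daily because of renal function (CrCl 50-59 at entry or 40-59 on study), the mandatory step after Grade 4 neutropenia lasting more than 7 days is a 0% reduction, against 50% for patients on 900 mg. The wholly uncovered case is a first episode with a total hold of 14 days or less; recurrence and longer holds are partly covered.

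The dose comparison follows directly from Tables 3 and 4. Calling 450 mg the counterpart of 900 mg rests on Table 4 itself. The number of patients is not in the documents and is likely small; the ranges above depend on an assumed share and an assumed event rate. This is a safety wording gap in a foreseeable, eligible group. It is worth correcting, and it has no claimed bearing on the efficacy analysis.

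**What to change.** In the Grade 4 neutropenia row, add that a patient already on 450 mg daily or less for renal function reduces to the next lower Table 4 regimen (for example 450 mg daily to 450 mg every 2 days) after Medical Monitor consultation. Where Table 4 has no lower regimen, and for patients under 17, who are dosed by body surface area, consultation alone would apply. Use the same wording in the three rows that say to consider the step. State that re-escalation may not exceed the Table 4 dose for the current CrCl. A lighter version would only require consultation before restarting such a patient.

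The cost is a few Table 3 rows in the next amendment, with the ethics review that Section 11.1.2 requires and a memo to the sites (about 80 per SAP Section 4.5.6.4). It needs no new tablet strength, split tablet, visit or test: the regimens are already in Table 4, and creatinine is already in the chemistry panel at on-treatment visits.

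The real downside is that the documents give no activity data below 450 mg daily, while Section 5.4 expects both drugs to be needed for activity. The exact lower dose is therefore for the sponsor's medical judgement.

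### Table 3 gives two unranked restart doses after QTc above 500 msec when QTc recovers and no other cause is found, and assigns no action to exactly 500 msec

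*Protocol*

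**What the plan says.** Protocol section 5.4, Table 3, sorts QTc prolongation into three bands: above 450 up to and including 480 msec, then "For QTc interval >480 msec and <500 msec", then above 500 msec. In the top band, electrolytes are corrected, both drugs are interrupted and medicines that may prolong QTc are stopped. Three sentences then govern what happens next:

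- The first turns on recovery of the interval: "If the QTc interval improves to ≤470 msec just prior to the start of the next cycle, resume nanatinostat/valganciclovir at the initial dose".
- The second turns on cause and makes no mention of recovery: "If no other cause of QTc prolongation is identified, reduce dose of nanatinostat to 10 mg once daily, days 1-4/7".
- The third is a fallback whose condition is left unstated: "Otherwise continue to hold nanatinostat/valganciclovir for as long as necessary".

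The initial nanatinostat dose is 20 mg once daily on Days 1 to 4 of each week (section 5.1.3).

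Three general rules in section 5.4 also bear on the restart:

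- Dose adjustments, other than valganciclovir changes for renal function, "must be approved by the Medical Monitor or Sponsor prior to implementing".
- On long holds: "If the dose is held for more than 14 days, the Investigator should consult with the Medical Monitor before dosing resumes".
- For a patient who has had several interruptions or "has had to interrupt for more than 14 days, a dose reduction should be considered".

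**The concern.** The first two sentences have different triggers: one is recovery of the interval, the other is the absence of another cause. The triggers can both be true. When they are, one sentence gives 20 mg and the other gives 10 mg, and no linking word makes either an exception to the other. Two investigators following the table could restart the same patient at doses that differ twofold, in the most serious QTc band. The protocol itself notes that QTc prolongation has been seen with other drugs of this class (section 1.3.2).

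The boundary problem is separate and smaller. The band below stops short of 500 and the top band starts above it, so a reading of exactly 500 msec has no stated action. The neighbouring actions differ: reduce nanatinostat to 10 mg, or interrupt both drugs.

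**Working it through.** No sample size, power or error rate depends on this row, so the check is one of logic plus simple day counts.

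**1. Bands.** Test values against the three printed ranges.

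| QTc (msec) | Band that applies |
|---|---|
| 480 | >450 to ≤480 |
| 481, 499 | >480 to <500 |
| 500 | none |
| 501 | >500 |

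**2. The row above 500 msec.** Cross recovery (≤470 msec before the next cycle) with whether another cause was found, and list what the first two sentences trigger.

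| Recovered | Other cause found | Resume sentence | Reduce sentence |
|---|---|---|---|
| yes | yes | 20 mg | not triggered |
| yes | no | 20 mg | 10 mg |
| no | yes | not triggered | not triggered |
| no | no | not triggered | 10 mg, taken alone |

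The second line is the conflict. It remains whichever sentence the closing fallback, "Otherwise continue to hold nanatinostat/valganciclovir for as long as necessary", is attached to. The fourth line is settled by context. Dosing is already interrupted, ≤470 msec is the only resumption test in the row, and the matching fallback in the band below, "Otherwise continue nanatinostat at 10 mg once daily", applies when QTc has not recovered. An unrecovered patient therefore stays on hold.

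**3. Size of the dose difference.** Dosing days per 28-day cycle: 4 days per week × 4 weeks = 16. Nanatinostat per cycle: 16 × 20 mg = 320 mg, or 16 × 10 mg = 160 mg.

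**4. Which restarts the general rules reach.** Approval applies to a dose adjustment and has no minimum hold, so moving to 10 mg is always covered. Restarting at the initial dose is not plainly an adjustment. Section 5.4 also requires Medical Monitor approval to re-escalate, but a patient held and then restarted at 20 mg was not reduced first. That leaves the 14-day consultation.

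The nominal hold from an ECG on cycle day d to Day 1 of the next cycle is 29 − d days:

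- Scheduled on-treatment ECGs outside Cohort 3a are Stage 1 only and fall on Day 1 or Day 4 (section 6.1, Table 5 and its footnotes). 29 − 1 = 28 and 29 − 4 = 25. Both exceed 14, so consultation applies.
- An ECG may also be done when clinically indicated (section 7.3.2.8). From Day 15 onward, 29 − 15 = 14 or fewer, so consultation is not triggered.
- In Cohort 3a, responders who continue monotherapy go from the Day 43 ECG to Day 57: 57 − 43 = 14. It is 57 − 46 = 11 if the ECG is on Day 46, as Table 5 footnote o has it. Visits carry a ±3-day window, and an ECG on Day 40 gives 57 − 40 = 17, which does trigger consultation.

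The uncovered case is therefore a 20 mg restart after a hold of 14 days or less.

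**The case against.** The strongest reply is that one reading fits every case. The row states a general rule (recovered: initial dose), then a narrower one (no other cause: 10 mg), then a fallback (not recovered: hold). If 20 mg won whenever QTc recovered, the 10 mg sentence would have nothing to do for recovered patients, and unrecovered patients are on hold anyway. This is probably what the authors intended. But the row does not say so, and the band directly below returns patients to the initial dose on recovery alone, with no test of cause. An investigator who carries that logic upward would restart at 20 mg.

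It is also fair to say that exposure is limited. Entry excludes QTcF above 480 msec, listed QT-prolonging antiarrhythmics are prohibited, and QTc prolongation is not among the dose-limiting toxicities in section 1.2.1.2 or the common events in section 1.2.4. All of this stands, and it is why the point is minor.

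A reader might go further and infer that the row sends unrecovered patients back on drug at 10 mg, or that nothing stands between a recovered patient and a full-dose restart. The documents support neither. Context keeps the unrecovered patient on hold, any reduction needs approval, and long holds need consultation. Nor is the whole of Cohort 3a exposed: the Day 57 count is nominal and concerns only responders who continue monotherapy.

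**Conclusion.** Wrong as written, and minor. One patient state, recovered to 470 msec or below with no other cause, carries two unranked doses, and one boundary value, 500 msec, carries no action. The safeguards name who decides, but they do not say which dose applies. The part they do not clearly reach is a 20 mg restart after a hold of 14 days or less.

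The documents give no expected number of patients above 500 msec, so the frequency cannot be stated. A reader might infer some effect on response rate, duration of response or error rates. Nothing in the documents shows one, and none is claimed. The finding rests on the comparison signs being as printed. A lost equals sign at 500 is possible, but the less-than-or-equal signs at 480 and 470 survive in the same row. The day counts are nominal.

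**What to change.** Reword the top band of the QTc row in the next amendment, with the sponsor confirming that the exception reading is intended. The content would be:

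- Applies to QTc of 500 msec or more. Correct magnesium and potassium, stop medicines that may prolong QTc, and interrupt both drugs, as now.
- QTc at or below 470 msec immediately before the next cycle, another cause identified: restart both drugs at the initial dose.
- QTc at or below 470 msec immediately before the next cycle, no other cause identified: restart with nanatinostat at 10 mg once daily on Days 1 to 4 of each week.
- QTc still above 470 msec: keep holding both drugs.

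Two details matter. The present timing, just before the next cycle, must stay, because dropping it would allow a mid-cycle restart and loosen the rule. The second line should turn on a cause having been identified, without adding that it was corrected; otherwise a recovered patient with an uncorrected cause would have no instruction.

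The cost is one table row. No new procedure or data item is needed. The QTcF categories in SAP section 4.6.5.2 are for reporting only and can stay as they are.
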